## 4.4 PERMISSIBLE AND PROHIBITED MEDICATIONS/TREATMENTS

### 4.4.1 Permissible Medications and/or Treatments

Therapy considered necessary for the subject's welfare may be given at the discretion of the Investigator, including but not limited to medications for other conditions (i.e., hypertension, diabetes, etc.), and treatment of adverse events (AEs). Medications should be taken consistently throughout the study and at the Investigator's discretion.

#### 4.4.1.1 Anesthesia

Local anesthesia may be used in the area of treatment at the discretion of the Investigator/Injector. Since the product contains lidocaine no other injectable anesthesia is expected to be used. The type of anesthesia used and dose of anesthesia during the treatment is at the clinical judgment of the Investigator/Injector. Anesthesia use elsewhere is prohibited.

The type, drug, dose and administration method of anesthesia shall be recorded. Anesthesia is to be administered according to local site practice.

#### 4.4.1.2 Rescue Medications

Although several authors have reported that hyaluronidase (Vitrase™ or Amphadase®) is effective to reverse the effects of misplaced or excess HA-based dermal fillers, no product has been approved for this indication. Administration of hyaluronidase is considered to be

“off-label” and has not been provided as a part of the study regimen and should not be performed during this study. However, if in the Investigator’s judgment it is deemed to be necessary to inject hyaluronidase for the safety of the subject, then the Investigator may inject at his/her discretion, capturing this information as a concomitant medication.

#### **4.4.1.3 Acceptable Contraceptive Methods**

Women of childbearing potential are required to practice a reliable method of contraception throughout the study. The following methods of contraception, if properly used, are generally considered reliable: oral contraceptives, patch contraceptives, injection contraceptives, male condom with intra-vaginal spermicide, diaphragm or cervical cap with spermicide, vaginal contraceptive ring, intrauterine device, surgical sterilization (bilateral tubal ligation), vasectomized partner, or sexual abstinence.

The Investigator and each subject will determine the appropriate method of contraception for the subject during the participation in the study.

#### **4.4.2 Prohibited Medications/Treatments**

The decision to administer a prohibited medication/treatment will be made with the safety of the study participant as the primary consideration. When possible, the Sponsor or Sponsor’s representative should be notified before a prohibited medication/treatment is administered.

Prior to attending study visits, subjects must not apply facial cosmetics.

For information regarding medications requiring washout prior to treatment, see *Section 6.1.3: Washout of Prohibited Medications/Treatments*.

##### **4.4.2.1 Anticoagulant Medications**

Subjects must not initiate a regimen of anti-coagulation therapy (e.g., warfarin), NSAIDs or other substances known to increase coagulation time (e.g., herbal supplements with garlic or ginkgo biloba) for 3 days following the procedure.

##### **4.4.2.2 Facial Procedures/Treatments**

Subjects must not undergo any type of facial plastic or reconstructive surgery, dental or cosmetic procedure [e.g., dental implant, new dentures, face-lift, resurfacing (laser, photomodulation, intense pulsed light, radio frequency, dermabrasion, chemical peel, or other ablative or non-ablative procedures), tissue augmentation with dermal fillers or fat injections, BOTOX® Cosmetic injections, or mesotherapy] anywhere in the lower face (below the orbital rim), neck, and oral cavity at any time during the study.

##### **4.4.2.3 Special Diet or Activities**

Within the first 24 hours after filler treatment, on V1, if a Touch-up treatment is performed on V2, or retreatment at V6, subjects should avoid strenuous exercise, extensive sun or heat exposure and alcoholic beverages. Exposure to any of the above may cause temporary redness, swelling, and/or itching at the injection sites.

## 5 TREATMENT

### 5.1 INVESTIGATIONAL PRODUCT

Juvéderm® VOLIFT™ with Lidocaine injectable gel is a sterile, biodegradable, non-pyrogenic, viscoelastic, clear, colorless, homogeneous gel implant (dermal filler). It consists of [REDACTED] formulated to a concentration of 17.5 mg/mL and [REDACTED] lidocaine in a physiologic buffer.

Commercial grade product will be provided by Allergan for use in this study, at no cost to the subject

#### 5.1.1 Blinding and Randomization

This is an open-label, single-arm study. Thus, blinding and randomization methods will not be implemented.

### 5.2 STORAGE, HANDLING AND DESTRUCTION

#### 5.2.1 Storage

[REDACTED]

[REDACTED]

### 5.3 TREATMENT ADMINISTRATION

The Investigator will determine the appropriate volume of Juvéderm® VOLIFT™ with Lidocaine to be injected to augment the lips (e.g., add fullness). It is anticipated that the volume of Juvéderm® VOLIFT™ with Lidocaine to be injected for lip augmentation will not exceed 3.0mL total per patient.

Clinical Study Protocol: CMO-MA-FAS-0512

---

Full details for the injection of Juvéderm® VOLIFT™ with Lidocaine will be provided in the *Juvéderm® VOLIFT™ with Lidocaine Directions for Use (Appendix 1)*.

For information on use of local anesthesia and use of rescue medications, refer to *Section 4.6.1.1* and *Section 4.6.1.2*, respectively.

## 6 STUDY VISIT SCHEDULE AND PROCEDURES

### 6.1 PATIENT ENTRY PROCEDURES

Prospective patients as defined by the criteria in *Sections 4.2 (Inclusion Criteria)* and *4.3 (Exclusion Criteria)* will be considered for entry into this study.

#### 6.1.1 Informed Consent

The study will be discussed with the patient. The subject must give written informed consent subject prior to the performance of any study-related procedures, inclusive of screening procedures, or change(s) in treatment, e.g. washout of medications.

See *Section 11.6: Informed Consent* for additional information and requirements regarding informed consent.

#### Informed Consent Extension to Follow-up

[REDACTED]

#### 6.1.2 Subject Number

All subjects who provide informed consent will be assigned a subject number [REDACTED]

#### 6.1.3 Washout of Prohibited Medications/Treatments

[figure not shown]
If washout of any medications is required, the subject must provide written informed consent before the washout can commence.

*Table 6.1* lists the medications/treatments that are prohibited during the study and the length of time that must pass between the medication/treatment and treatment in the study.

For additional information/examples of specific treatment/procedures, refer to *Section 4.3 (Exclusion Criteria)*.

Study treatment may be delayed as necessary to accommodate the washout period. If treatment is delayed beyond the 14-day screening period (see *Table 1.1: Schedule of Study Procedures, Treatments, and Assessments*), screening procedures are to be repeated as necessary to confirm participation eligibility. The inclusion/exclusion criteria must be reassessed and the patient eligibility confirmed prior to study treatment.

**Table 6.1 Washout Periods of Medications/Treatment**

[figure not shown]

[figure not shown]
**6.1.4 Subject Enrollment**

A subject is considered “entered” into the trial after the subject has signed the Informed Consent Form (ICF) and a subject number has been assigned.

A subject is considered “enrolled” after confirmation of participation eligibility and treatment has occurred.

**6.2 DESCRIPTION OF STUDY VISITS**

[figure not shown]

[figure not shown]

## **6.2.2 Treatment**

The Treatment visit is considered as Day 1. Subjects confirmed to be eligible for participation during the screening period will receive study treatment as described in *Section 5.3: Treatment Administration*

### **6.2.2.1 Prior to Study Treatment**

**6.2.2.2 Study Treatment**

Administer study treatment as described in *Section 5.3: Treatment Administration*

**6.2.2.3 Post Study Treatment**

[Redacted text block]

[figure not shown]
[Redacted text block]

**6.2.3 Day 14 Visit (Touch-up Treatment, if required)**

[Redacted text block]

**6.2.3.1 For All Subjects**

- Record concomitant medications/procedures.
- Record AEs.

[figure not shown]

Clinical Study Protocol: CMO-MA-FAS-0512

[figure not shown]
---

[figure not shown]
- Investigator and subject determine if Touch-up Treatment is required.

#### **6.2.3.2 For Subjects Receiving Touch-Up Treatment**

[figure not shown]

#### **6.2.4 Day 30 Visit**

### 6.2.8 Unscheduled Visits

Each time the subject returns to the study site, the Investigator (or designee) will solicit and record information about ISRs, AEs, and concomitant medications/procedures. An interim or unscheduled visit may replace a scheduled visit if it occurs within the acceptable visit window for a scheduled visit or if the scheduled visit was missed. All applicable procedures should be performed.

### 6.2.9 Early Discontinuation

[figure not shown]
Subjects may withdraw consent for participation or be withdrawn from the study at any time without jeopardy to future medical care. See *Section 8: Discontinuation Criteria* regarding reasons for discontinuations.

[figure not shown]
If a subject exits the study prior to month 6, the subject will be asked to attend an end of study visit and have all assessments performed and clinical data collected as required by the month 6 visit. If a subject does not consent to the extension of the study at completion of their 6-month visit, this will be recorded in the database.

Participation eligible subjects who withdraw before any treatment is given may be replaced by another suitable subject. The subject number will not be reassigned to a different subject.

## 6.3 POST-TREATMENT INSTRUCTIONS FOR SUBJECTS

Prior to leaving the study site, the subject's next study visit should be scheduled and a reminder card provided to the subject. If possible, the remainder of the visits should be scheduled at the end of the Day 14 visit.

## **7 METHODS OF ASSESSMENT AND ENDPOINTS**

### **7.1 STUDY PROCEDURES**

#### **7.1.1 Demographic Data**

Subject demographic data will be collected at the Screening Visit.

These data include age, gender, and Fitzpatrick type.

#### **7.1.2 Medical History**

Medical history will be obtained from each subject at the Screening Visit.

Medical history includes pertinent surgical history and a detailed history of prior aesthetic procedures with start and stop dates, if applicable, as well as any discontinuations due to intolerability or toxicity.

#### **7.1.3 Concomitant Medications/Procedures**

Concomitant medication/procedure status shall be collected at all visits. Concomitant medications include prescription medications, dietary supplements, over-the-counter medications, and oral herbal preparations.

Clinical Study Protocol: CMO-MA-FAS-0512

A list of concomitant medications/procedures will be collected at the screening visit. Data collected shall be medication/treatment name, dose, frequency, start date, stop date (if applicable). All medications or treatments received within 30 days before the screening visit shall be recorded. Medications/procedures received more than 30 days before screening and in the Investigators judgment is pertinent to this study, should also be recorded.

Following treatment at Day 1, subjects will be asked at each subsequent study visit whether any new medication/procedures have been administered or of any changes in dosage or frequency, have occurred since the previous visit. All concomitant medications and procedures will be recorded on eCRFs.

### 7.1.4 Fitzpatrick Skin Phototype

The subject’s Fitzpatrick skin phototype will be determined at the screening visit using the parameters listed in *Table 7.1*.

**Table 7.1 Fitzpatrick Skin Phototype**

Skin type	Typical Features	Tanning ability
I	Pale white skin, blue/green eyes, blond/red hair	Always burns, does not tan
II	Fair skin, blue eyes	Burns easily, tans poorly
III	Darker white skin	Tans after initial burn
IV	Light brown skin	Burns minimally, tans easily
V	Brown skin	Rarely burns, tans darkly easily
VI	Dark brown or black skin	Never burns, always tans darkly

### 7.1.5 Urine Pregnancy Test

The urine pregnancy test will be performed at the screening visit and prior to administration of any study treatment (Day 1 and Day 14, if applicable and at retreatment at Month 12). The urine pregnancy test will be performed only for women of childbearing potential. The woman’s childbearing status must be clearly reported in the source documentation.

[figure not shown]
Women of childbearing potential must have a negative pregnancy test before any study treatments are given. See *Figure 7.1* to determine pregnancy status.

Women who are determined to have negative pregnancy test results may continue in the study and receive study treatments as applicable.

- Women who are determined to have positive pregnancy test results prior to initial treatment must be informed of their pregnancy status and discontinued from the study as screen failures.
- Women who are determined to have positive pregnancy test results after receiving the initial treatment must be withdrawn from the study and have their pregnancy followed and reported per *Section 9.2.4: Pregnancy*.

- Women who are determined to have positive pregnancy test at re-treatment will not be eligible for the retreatment, and have their pregnancy followed and reported per *Section 9.2.4: Pregnancy*.

[figure not shown]
**Figure 7.1 Pregnancy Test Results**

Neg=negative; Pos=positive

**7.1.6 Photographs**

Facial photographs will be captured prior to study treatments and immediately after. Additional images will be captured at the Day 30, Month 3, Month 6, Month 12 and any subsequent visits. Images will be used by the investigator and subject for the facial assessments.

Clinical Study Protocol: CMO-MA-FAS-0512

---

[REDACTED] 3D photographs will also be taken for each subject to aid in facial assessments and measure the volume change in the lips.

Equipment and training for the capturing of images will be provided by a vendor selected by Allergan.

### **7.1.7 Injection Site Reaction (ISR) 30-Day Diary**

The ISR 30-Day Diary will be completed by the subject beginning on the day of treatment and for 30 consecutive days. [REDACTED]

#### **7.1.7.1 Day 1 Visit (Treatment)**

The subject will be provided with an ISR Diary on the day of the study treatment. [REDACTED]

#### **7.1.7.2 Day 14 Visit (Touch-up, if required)**

#### **7.1.7.3 Day 30 Visit**

## **7.2 EFFICACY MEASURES**

### **7.2.1 Lip Fullness Scale (LFS2)**

The Lips Fullness Scale 2 (LFS2) is an Investigator assessment of overall lip fullness measured by a 5-point scale (see *Appendix 3: Lip Fullness Scale 2 (LFS2)*). The Investigator will use the LFS2 to perform a live assessment of the subject at the visits specified in *Table 1.1: Schedule of Study Procedures, Treatments, and Assessments*. Photographic images will be collected to capture the subject status at the time of the live assessments.

## **7.2.2 Oral Commissures Severity Scale (OCSS)**

The Oral Commissure Severity Scale (OCSS) is an Investigator assessment measured on a 4-point scale (see *Appendix 4: Oral Commissure Severity Scale (OCSS)*). The Investigator will use the OCSS to perform a live assessment of the subject at the visits specified in *Table 1.1: Schedule of Study Procedures, Treatments, and Assessments*. Photographic images will be collected to capture the subject status at the time of the live assessments.

## **7.2.3 FACE-Q Satisfaction with Lips**

The subject will assess satisfaction using the 10 items on the Satisfaction with Lips questionnaire of the FACE-Q (see *Appendix 5*). The responses to the items are combined to create a scale score that ranges from 0 to 100. This FACE-Q was designed to assess the impact of treatment from the subject's perspective.

## **7.2.4 Global Aesthetic Improvement Scale (GAIS) Questionnaires**

### **7.2.4.1 GAIS Investigator**

Investigator's assessment of global facial aesthetic improvement as measured by the 5-point GAIS (see *Appendix 6: Global Aesthetic Improvement Scale (GAIS)*).

### **7.2.4.2 GAIS Subject**

Subject's assessment of global facial aesthetic improvement as measured by the 5-point GAIS (see *Appendix 6: Global Aesthetic Improvement Scale (GAIS)*).

## **8 DISCONTINUATION CRITERIA**

### **8.1 DISCONTINUATION OF THE STUDY**

The Investigator or Allergan, may terminate the Investigator's participation in this study after submission of a written notice. Allergan may terminate the study at any time for any reason.

### **8.2 DISCONTINUATION OF SUBJECTS**

A subject may voluntarily withdraw or the Investigator may withdraw the subject at any time without prejudice to the subjects' future medical care by the investigator or institution. It is the responsibility of the site Investigator to discontinue a subject's participation when the subject's health or wellbeing is threatened by continuation in the study.

For any subjects who withdraw from the study, the date and reason for withdrawal should be recorded on the eCRF. If an AE or ISR is ongoing at the time of the withdrawal, the Investigator will attempt to follow the subject until the AE or ISR has resolved or stabilized.

#### **8.2.1 Withdrawal Criteria**

The following circumstances shall result in a subject's discontinuation from the study:

- the subject undergoes repeat treatment other than Touch-up at Day 14 or study retreatment
- If subject is administered any of the prohibited procedures listed as exclusionary in Section 4.3
- Subject is lost to follow-up. Subjects may be withdrawn if they do not return for follow-up visits. If a subject fails to return for one or more scheduled study visits, the Investigator will attempt to contact the subject to determine and document the reason the subject has failed to return and to encourage compliance with the study visit schedule.

The following circumstances may result in a subject's discontinuation from the study:

- AEs or serious adverse events (SAEs) that render the subject unable to continue study participation
- Protocol violation
- Non-compliance with study requirements
- Discretion of Investigator (must document reason on eCRF)
- Progressive injury (at the discretion of the Investigator)
- There are changes in the subject's condition that render the subject unacceptable for further participation in the judgment of the Investigator
- A subject is unable to physically or mentally tolerate the use of the test treatment

## 9 ADVERSE EVENTS

Throughout the course of the study (from the date of informed consent), all AEs will be monitored and recorded in source documents and on the AE eCRF. If an AE occurs, the first concern will be the safety of the study participant. All AEs related to study treatments or procedures will be followed until resolved or stabilized based on the Investigator's clinical judgement.

### 9.1 DEFINITIONS

#### 9.1.1 Adverse Events (AE)

The reference safety data will be the current VOLIFT with Lidocaine instructions for use.

According to EN ISO 14155:2011 an AE is any untoward medical occurrence, unintended disease or injury, or untoward clinical signs (including abnormal laboratory findings) in subjects, users or other persons, whether or not related to the investigational medical device or the comparator device.

NOTE 1: This definition includes events related to the investigational medical device or the comparator.

NOTE 2: This definition includes events related to the procedures involved.

NOTE 3: For users or other persons, this definition is restricted to events related to investigational medical devices.

Adverse events are collected once informed consent has been obtained, regardless of whether or not the subject has been administered study treatment. Disease signs and symptoms that existed prior to the study treatment are not considered AEs unless the condition recurs after the subject has recovered from the pre-existing condition or the condition worsens in intensity or frequency during the study.

All AEs ongoing at the exit visit must be followed until resolved or stable, based on the investigator's clinical judgment.

#### 9.1.2 Serious Adverse Events (SAE)

According to EN ISO 14155:2011 an SAE is an AE that:

- Led to death,
- Led to a serious deterioration in the health of the subject that
  - resulted in a life-threatening illness or injury, or
  - resulted in a permanent impairment of a body structure or a body function, or
  - required in-subject hospitalisation or prolongation of existing hospitalisation, or
  - resulted in medical or surgical intervention to prevent permanent impairment to body structure or a body function.

- Led to foetal distress, foetal death or a congenital abnormality or birth defect.

NOTE: Planned hospitalisation for a pre-existing condition, or a procedure required by the CIP, without serious deterioration in health, is not considered an SAE. Allergan considers all cancer AEs as SAEs. Abortion is also considered an SAE except for elective abortion of a normal fetus.

(See *Section 9.3: Procedures for Reporting an SAE/SADE*).

Any pre-planned surgery or procedure should be clearly documented in the site source documents by the medically qualified Investigator at the time of the subject's entry into the study.

### **9.1.3 Adverse Device Effect (ADE)**

According to EN ISO 14155:2011 any AE related to the use of an investigational medical device, including those events resulting from insufficient or inadequate instructions for use, deployment, implantation, installation, or operation, or any malfunction of the investigational medical device.

NOTE 1: This definition includes AEs resulting from insufficient or inadequate instructions for use, deployment, implantation, installation, or operation, or any malfunction of the investigational medical device.

NOTE 2: This definition includes any event resulting from use error or from intentional misuse of the investigational medical device.

### **9.1.4 Serious Adverse Device Effect (SADE)**

According to EN ISO 14155:2011 a SADE is an ADE that resulted in any of the consequences characteristic of an SAE or that might have led to an SAE if

- a) suitable action had not been taken, or
- b) intervention had not been made, or
- c) circumstances had not been less fortunate.

SADEs will be handled under the SAE reporting system.

### **9.1.5 Unanticipated Serious Adverse Device Effect (USADE)**

According to EN ISO 14155:2011 a USADE is a serious adverse device effect which by its nature, incidence, severity or outcome has not been identified in the current version of the risk analysis report

NOTE: Anticipated serious adverse device effect (ASADE) is an effect which by its nature, incidence, severity or outcome has been identified in the risk analysis report.

### **9.1.6 Device Deficiency**

A device deficiency is defined in accordance with ISO 14155 as “inadequacy of a medical device with respect to its identity, quality, durability, reliability, safety, or performance.” Device deficiencies include malfunctions, use errors, and inadequate labeling.

If a device deficiency occurs, the Investigator will notify the Sponsor by email at the email address provided on the cover page of this protocol. Allergan shall review all device deficiencies and determine/document in writing whether they could have led to a SADE. These shall be reported to the regulatory authority as required by national regulations.

**9.1.7 Injection Site Reaction (ISR)**

ISRs following treatment with dermal fillers include redness, pain after injection, tenderness to touch, firmness, swelling, lumps/bumps, bruising, itching, discoloration, and other specified events. Subjects will maintain a diary record of the presence, location, frequency, severity, and duration of any ISR for 30 days after treatment (initial and Touch-up). (See *Section 7.1.7: Injection Site Reaction (ISR) 30-Day Diary* for further details).

ISRs that persist longer than 30 days (i.e., ongoing at the end of the diary period) will be reported as AE and followed as described in *Section 9.2: Procedure for Reporting Adverse Events*. If an ISR is ongoing or appears 30 days after the patient’s last study visit, it will be followed up by Allergan Product Surveillance separate from this study protocol.

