**SIDE EFFECTS**

The patients must be informed that there are potential side effects associated with implantation of this product, which may occur immediately or may be delayed. These include, but are not limited to:

- Inflammatory reactions (redness, oedema, erythema, etc.) which may be associated with itching or pain on pressure or both, occurring after the injection. These reactions may last for a week. In particular, it has to be noticed that injection in the mucous membrane may cause more oedema and bruising due to the specific physiology of these tissues. Besides, a preventive anti-inflammatory treatment by a medical practitioner can be recommended.
- Haematomas.
- Induration or nodules at the injection site.
- Staining or discolouration of the injection site.
- Poor effect or weak filling effect.

- Cases of necroses in the glabellar region, abscesses, granuloma and immediate or delayed hypersensitivity after hyaluronic acid and/or lidocaine injections have been reported. It is therefore advisable to take these potential risks into account.

- Patients must report inflammatory reactions which persist for more than one week, or any other side effect which develops, to their medical practitioner as soon as possible. The medical practitioner should use an appropriate treatment.

- Any other undesirable side effects associated with injection of **Juvéderm® VOLIFT™ with Lidocaine** must be reported to the distributor and/or to the manufacturer.

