#### **9.5. Injection Site Reaction 30-Day Diary**

ISRs following treatment with dermal fillers include redness, pain after injection, tenderness to touch, firmness, swelling, lumps/bumps, bruising, itching, discoloration, and other specified events. Subjects will maintain a diary record of the presence, location, frequency, severity, and duration of any ISR for 30 days after treatment (initial and Touch-up). An example of the ISR 30-Day Diary is available in Protocol Appendix 2.

The ISR 30-Day Diary will be completed by the subject beginning on the day of treatment within 60 minutes post-treatment and daily for 30 consecutive days. Subjects who receive Touch-up treatment will return the original ISR 30-Day Diary completed from initial treatment to Day 14 visit. A new ISR 30-Day Diary will be provided at Day 14 to subjects receiving Touch-up treatment. The subject will begin using the new ISR 30-Day Diary to capture any ISRs that occur following Touch-up treatment with Day 1 of the new ISR 30-Day Diary completed within 60 minutes post-treatment.

ISRs that persist longer than 30 days (i.e., ongoing at the end of the diary period) will be reported as AEs.

ISR 30-Day Diary entries will be listed for the SS.

[figure not shown]

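### The visible text makes duration the only trigger that turns an injection site reaction into an AE, so severe or treated non-serious reactions of up to 30 days can stay in a diary that is listed but never summarised

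*Protocol*

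**What the plan says.** **The ISR rule.** Protocol 9.1.7 lists the reaction types (redness, swelling, bruising, lumps and so on), has subjects keep a diary for 30 days after the initial and touch-up injections, and then says: "ISRs that persist longer than 30 days (i.e., ongoing at the end of the diary period) will be reported as AE". SAP 9.5 has the same rule: "ISRs that persist longer than 30 days (i.e., ongoing at the end of the diary period) will be reported as AEs". Neither section, as far as it can be read, mentions severity, treatment, discontinuation or seriousness as a reason to record an ISR as an AE.

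**The general AE rules.** Under Protocol 9.1.1, "an AE is any untoward medical occurrence, unintended disease or injury, or untoward clinical signs (including abnormal laboratory findings) in subjects, users or other persons". A note adds: "This definition includes events related to the procedures involved". No minimum duration is set and ISRs are not excepted. The opening of Protocol section 9 requires that "all AEs will be monitored and recorded in source documents and on the AE eCRF". Protocol 9.1.2 builds seriousness on AE status ("According to EN ISO 14155:2011 an SAE is an AE that" has one of the listed outcomes). Protocol 9.1.4 does the same for serious device effects, and 9.3 requires SAEs to be reported within 24 hours.

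**The reporting plan.** SAP section 9 names two bases for assessing safety: AE reports and the ISR diary. SAP 9.3 generally limits the summary tables to treatment-emergent AEs (TEAEs). SAP 9.5 plans only a listing of the diary.

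**The concern.** The general definition makes a short local reaction an AE at once. The ISR rule suggests that it becomes one only when it has lasted long enough. No visible sentence says which governs, so two sites seeing the same reaction could record it differently: one on the AE form with severity and causality, the other in the diary alone.

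The event types at stake matter for a lip filler. Marked swelling or bruising that needs a prescription and settles in two weeks is a clinically relevant local reaction. If it stays in the diary, it does not contribute to the TEAE, related-TEAE, maximum-severity or discontinuation tables. The reported AE rate would then depend partly on how each site read 9.1.7.

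**Working it through.** No arithmetic on power or rates applies. The check compares the passages and counts the planned outputs.

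**1. Can the sections be read together?** If every ISR were already an AE under Protocol 9.1.1, the 30-day sentence in 9.1.7 would add nothing. A site will therefore tend to read it as a limit, with shorter ISRs staying in the diary. Other sections support that reading by naming ISRs and AEs as separate items: Protocol 6.2.8 (unscheduled visits), 8.2 (events ongoing at withdrawal) and 9.2.2 (ISR severity is defined in the diary, apart from the AE severity scale).

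**2. Which reactions are affected?**

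| ISR resolved within 30 days and before the diary ends | Protocol 9.1.1 | Visible ISR rule | Position |
|---|---|---|---|
| Meets a 9.1.2 seriousness criterion | AE | No trigger | Covered by 9.1.2, 9.1.4 and 9.3, none of which excepts ISRs |
| Severe or medically treated, not serious | AE | No trigger | Unresolved conflict; site decides |
| Mild and untreated | AE | No trigger | Same conflict, but diary-only recording is a defensible design choice |

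The firm gap is the second row.

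**3. What does the SAP produce for a diary-only ISR?** From the SAP indexes of tables and listings:

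- TEAE summary tables: 14.3.1.1 to 14.3.1.11, so 11 tables, none fed by the diary.
- Table 14.3.1.12 covers device deficiencies.
- ISR summary tables: 0.
- ISR listings: 1 (16.2.7.4).

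**4. A knock-on effect.** Table 14.3.4.4 compares injected volume between subjects with and without a TEAE. The DFU (Protocol Appendix 1, Method of Use) warns that excessive volume can lead to severe oedema, and swelling is a listed ISR. A subject whose only event was swelling kept in the diary would fall in the no-TEAE group of the table best placed to show a link with volume.

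**5. Is the duration rule itself clear?** It has two halves, which can disagree:

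- An ISR that starts on diary Day 25 and is still present on Day 30 has lasted 30 − 25 + 1 = 6 days. It is ongoing at the end of the diary, but not longer than 30 days.
- With a touch-up, SAP 9.5 starts a new diary at Day 14. If touch-up falls on study day 14, that diary ends on study day 14 + 29 = 43. A reaction to the first injection lasting from study day 1 to study day 35 has lasted 35 days, yet is not ongoing when the second diary ends.

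**6. What the diary captures.** Protocol 9.1.7 names presence, location, frequency, severity and duration. Causality, seriousness and treatment given are not in that list, so the diary as described does not replace an AE record.

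**The case against.** The strongest reply is that nothing is excluded. Protocol 9.1.7 does not say that only long-lasting ISRs are AEs, and the definition in 9.1.1, "any untoward medical occurrence, unintended disease or injury, or untoward clinical signs", already takes in the shorter ones. Once such a reaction is on the AE form, it enters the TEAE tables. This reply stands in full for serious reactions. A reader might infer that a reaction leading to hospital care in week 1 escapes SAE reporting because it is not yet an AE. The documents do not support that: 9.1.2, 9.1.4, Table 9.1 and 9.3 carry no ISR exception and no minimum duration, so a reaction meeting a 9.1.2 criterion is reportable within 24 hours.

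Two other inferences also go too far. One is that all ISRs of up to 30 days are outside the AE tables. Some may be recorded under 9.1.1, and the gloss on diary end catches some that have lasted less than 30 days. The other uses the DFU, which says "Patients must report inflammatory reactions which persist for more than one week" to their practitioner, as if it set a competing AE threshold. It is a patient-to-practitioner instruction about inflammatory reactions, not an AE recording rule, and it gives no duration for haematoma, nodules or discolouration.

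The data are also not lost. Diary entries are listed, treatments are captured as concomitant medications, and reasons for discontinuation are summarised under SAP 7.1. That is true, but no planned summary connects any of these to an ISR.

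Finally, 9.1.7 refers to Protocol 7.1.7 for details. Parts of 7.1.7 and of the visit procedures are redacted or not shown, as is the Appendix 2 diary. An escalation instruction may sit there. SAP 9.5, which is largely readable and describes diary handling in detail, contains none.

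**Conclusion.** The concern holds in limited form. In the visible text, duration is the only stated route from ISR to AE, and it is not reconciled with the general AE definition. Serious short ISRs are covered. Severe or medically treated non-serious ISRs of up to 30 days can be kept in the diary alone, where they appear in one listing and no summary table, and sites may classify them differently.

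The size in terms of outputs is definite: a diary-only ISR is absent from 11 TEAE tables and does not place its subject in the TEAE group of Table 14.3.4.4. The size in terms of subjects is unknown, because the documents give no ISR frequency or severity distribution.

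The conclusion assumes that some sites will read the 30-day sentence as a limit, and that the redacted or missing material does not already contain an escalation rule. If it does, the classification conflict falls away for the reactions that rule covers. The lack of any ISR summary table would remain.

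**What to change.** 1. Amend Protocol 9.1.7 and SAP 9.5 so that they agree with Protocol 9.1.1, 9.1.2 and 9.3. Suggested text: An ISR that meets a criterion in 9.1.2 is recorded as an SAE. An ISR that is rated severe, needs medical treatment or leads to discontinuation is recorded as an AE. Both apply from the onset date and regardless of duration. Other ISRs are recorded as AEs under the 30-day rule. If 7.1.7 or the diary already holds such an instruction, refer to it in both sections.
2. In the same edit, state how the two halves of the 30-day rule apply when a touch-up starts a new diary.
3. Add one ISR summary table to the SAP for the Safety Analysis Set, giving incidence, maximum severity and duration by reaction type. It uses diary data already collected.

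Item 1 needs a short protocol amendment, a note to sites and a sentence in the SAP. Item 3 needs only a SAP change. The downside is a few more AE forms, one more table and a slightly higher reported AE rate. No treatment or visit changes.
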